3.2.2 Secondary endpoint(s)

- Number of treatment related AEs
- Number of systemic reactions
- Number of non-local adverse drug reactions
- Number of serious AEs (SAEs)
- Sum of pre-specified local adverse reactions (as specified in the primary endpoint) within the first 4-6 months of treatment in patients with history of Pollen Food Syndrome (PFS)
- Adherence to the first 4-6 months of treatment.

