3.1 Overall study design

[figure not shown]
This is a non-interventional, observational, multi-site, open-label, multi-national PASS to investigate the safety and tolerability of ITULAZAX in adult patients in a real-life setting in Germany, the Netherlands, Denmark, Sweden, Norway and Finland.

A total number of approximately 1000 patients (aged 18-65 years) are planned to be enrolled and to be prescribed ITULAZAX in accordance with the nationally approved SmPC [5] and normal clinical practice.

The study will be initiated in November 2019 and the patients are planned to be followed for 4-6 (4 on average) months. A total number of 3-4 visits with approximately 1-3 months in between are planned (Figure 1).

The study is a non-interventional PASS based on the investigator's prescription of ITULAZAX, for which reason the number of visits and the duration between the visits are only intended as a guide.

Figure 1 Study design

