3.5.2 Patient discontinuation

The patients will be advised that he/she have the right to discontinue from the study at any time without prejudice.

Furthermore, the patient may also be discontinued from the study at the discretion of the investigator, e.g. in case of AEs or treatment discontinuation.

In case of discontinuation, the investigator should attempt to collect any outstanding data, if possible. The investigator should inquire about the reason for discontinuation (adverse event, non-compliance with protocol or other) and specify this in the case report form (refer to Section 4).

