- If applicable and done in routinely use: Patient video (shown for information on SLIT-tablet treatment (no/not shown later in the study/yes, before the first administration, after first administration)
- First administration of SQ tree SLIT-tablet (date/time of application, anti-allergic premedication applied (no/yes), AEs (no/yes, if yes document on AE pages)
- First administration of other SLIT-tablets, allergen 1, allergen 2 (date/time of application, anti-allergic premedication applied (no/yes), AEs (no/yes, if yes document on AE pages), if applicable
- Assessments of AEs after first administration of ITULAZAX
- Assessments of AEs after first administration of the other SLIT-tablet, if applicable
- Schedule date for visit 2

3.7.2 Visit 2

The following procedures should be performed at visit 2:

- Assessment of AEs since last visit (incl. FU-information on previous AEs)
- Pregnancy (yes, no)
- Changes in relevant concomitant diseases and medical treatments
- Adherence estimate (average frequency of tablet intake, reasons for not taking the tablet)
- Allergy symptoms since last visit (nose, eyes, bronchial, skin)
- PFS-symptoms since last visit
- Symptomatic medication since last visit
- If applicable and done in routinely use: Antibody Responder Test (ART), (ART generally applied, if yes results IgE, IgG4, neg./pos., ART score)
- If applicable and done in routinely use: Fractional exhaled nitric oxide (FeNO) (result (ppb FeNO), if performed).
- If applicable and done in routinely use: Patient video
- First administration of other SLIT-tablets, allergen 1, allergen 2 (date/time of application, anti-allergic premedication applied (no/yes), AEs (no/yes, if yes document on AE pages), if applicable
- Schedule date for visit 3

3.7.3 Visit 3

The following procedures should be performed at visit 3:

- Assessment of AEs since last visit (incl. FU-information on previous AEs)

Template
TPL48761
Signature: OnPaper

NI Protocol

- Pregnancy (yes, no)
- Changes in relevant concomitant diseases and medical treatments
- Adherence estimate (average frequency of tablet intake, reasons for not taking the tablet)
- Allergy symptoms since last visit (nose, eyes, bronchial, skin)
- PFS-symptoms since last visit
- Symptomatic medication since last visit
- If applicable and done in routinely use: Fractional exhaled nitric oxide (FeNO) (result (ppb FeNO), if performed).
- If applicable and done in routinely use: Patient video

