7.2 Definition of analysis sets

All patients with at least one administration of ITULAZAX will form the All-Patients-treated set (Safety Set).

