7.4 Safety analysis

AEs as well as breakdown of AEs and treatment-related AEs (possibly related) according to seriousness, severity and causality will be summarised for AEs during administration (V1 to V4).

AEs will be summarised by MedDRA System Organ Classes and MedDRA Preferred Terms displaying number of patients, frequency of patients having AEs as well as number of AEs.

Missing data will not be replaced.

8 Protection of human subjects

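### Adherence over the first 4-6 months is liable to be overstated, because the protocol does not secure or count the untreated time of patients who stop ITULAZAX

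*Protocol*

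**What the plan says.** The endpoint in Section 3.2.2 covers a whole period: "Adherence to the first 4-6 months of treatment". Section 3.4 repeats it as adherence to the first 4 months and counts it among the measures suited to the safety and tolerability objective.

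The item collected at Visits 2, 3 and 4 (Sections 3.7.2 to 3.7.4) is "Adherence estimate (average frequency of tablet intake, reasons for not taking the tablet". Adherence has no row in the flow chart (Table 2) and is not listed in the follow-up assessments of Section 3.8.6.

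On stopping, Section 3.5.2 says that "the patient may also be discontinued from the study at the discretion of the investigator, e.g. in case of AEs or treatment discontinuation". It continues: "In case of discontinuation, the investigator should attempt to collect any outstanding data, if possible". The reason for discontinuation is to be entered in the case report form.

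For other immunotherapies and for concomitant medication, Section 3.7.1 lists start and end dates. For ITULAZAX, Sections 3.7.1 and 3.8.5 name only the date and time of first administration.

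Section 7.4 states "Missing data will not be replaced". The synopsis has the same sentence under statistical methods, not limited to safety data. The one analysis set, in Section 7.2, is everyone with at least one administration.

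**The concern.** The endpoint asks how much of a 4-6 month course was taken. The data describe how often tablets were taken in the interval before a visit that the patient attended. The two agree only if the time after a patient stops enters as no intake. A patient who stops and is then discontinued has no further scheduled visit, so that time may leave no record. The rule against replacing missing data can be read as forbidding an analyst to fill it in.

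The loss is unlikely to be random. The protocol's only discontinuation figure concerns adverse events, mainly irritation or swelling in the mouth or throat (Section 1.1), and swelling at these sites is the subject of the primary endpoint (Section 3.2.1). If patients who tolerate the tablet poorly leave, later visits look better because of who remains. A reader who takes the adherence figure as evidence of tolerability, as Section 3.4 invites, would be misled in the favourable direction.

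**Working it through.** The protocol gives no adherence figure, expected stopping rate or formal sample size calculation, so there is no stated result to reproduce. The arithmetic below is an illustration.

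**Inputs**
- d, the share who stop: 8%, from Section 1.1 (25 subjects on active treatment in TT-04 discontinued because of adverse events). Check: with 634 subjects randomised 1:1, 25 / (634/2) = 25/317 = 7.9%. This is an earlier trial and adverse events only. Values of 15% and 25% are assumptions.
- a, intake while on treatment: 90% (assumption), varied from 80% to 95%.
- f, the fraction of the course completed before stopping: 0.25 to 0.5 (assumption), extended down to 0.1 in the range.

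**Step 1: no stopper supplies data on untreated time.** The observed mean is a. This holds even if stoppers gave estimates before stopping, provided that their intake while treated was also a, because those estimates describe treated time only.

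**Step 2: untreated time counted as zero.** Whole-course adherence = a × [(1 − d) + d × f], and the gap = a × d × (1 − f).

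| d | f = 0.25 | f = 0.5 | Observed only |
|---|---|---|---|
| 8% | 0.90 × (0.92 + 0.020) = 84.6% | 0.90 × (0.92 + 0.040) = 86.4% | 90% |
| 15% | 0.90 × (0.85 + 0.0375) = 79.9% | 0.90 × (0.85 + 0.075) = 83.3% | 90% |
| 25% | 0.90 × (0.75 + 0.0625) = 73.1% | 0.90 × (0.75 + 0.125) = 78.8% | 90% |

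**Step 3: range at d = 8%.** The smallest gap is 0.80 × 0.08 × 0.5 = 3.2 points. The largest is 0.95 × 0.08 × 0.9 = 6.8 points.

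**Step 4: some stoppers supply an estimate that covers the untreated time.** Let k be the share who do. The observed mean is [a(1 − d) + k × d × f × a] / [(1 − d) + k × d]. With d = 8%, a = 90% and f = 0.25:
- k = 0: 90.0%, a gap of 5.4 points.
- k = 0.5: (0.828 + 0.009) / 0.96 = 87.2%, a gap of 2.6 points.
- k = 1: 84.6%, no gap.

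The direction is upward wherever k is below 1. The size depends on k, d and f, none of which the protocol gives for this study.

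**The case against.** The strongest reply is that the adherence calculation belongs to a statistical analysis plan, which is not at hand, and that the protocol says nothing false. It prescribes no average over attended visits and no restriction to completers. Patients who stop remain in the Safety Set, may keep attending, and have their earlier estimates counted. Outstanding data and the reason for discontinuation are to be sought, and Table 2 allows a withdrawal entry at any visit. Setting intake to zero after a known stop is derivation from recorded fact, not replacement of missing data. Local reactions are captured directly by the primary endpoint and by systematic adverse event collection, and no formal test rests on adherence.

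Much of this stands. A reader might infer that the protocol removes stoppers from the endpoint, that adherence will certainly be overstated, or that poor tolerability is hidden from the study. The documents support none of these. Section 7.2 keeps stoppers in the set, Section 3.5.2 makes discontinuation discretionary and asks for the outstanding data, and the adverse event data do not depend on adherence.

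Two things remain. First, an analysis plan can count zero intake from a stop date only if that date was collected, and the protocol does not name it. The electronic case report form may hold it, but nothing shown requires it. Second, the unqualified sentence on missing data sits in the protocol, so the protocol should say that it does not cover known non-intake. Estimates given before stopping do not close the gap, as step 1 shows.

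**Conclusion.** The concern holds as a conditional risk of upward bias. Followed as written, the protocol tends to lose the untreated time of patients who stop, while naming an endpoint that includes it. At 8% stopping the overstatement lies between 0, if every stopper supplies an estimate covering untreated time, and about 3 to 7 points if none does. With 90% intake on treatment and stopping a quarter to half way through, that means about 85-86% in place of 90%. The gap widens with more stopping. All inputs except the 8% are assumptions, and the 8% excludes stopping for other reasons. The study's adverse event results are not affected. The change is worth making because it is cheap and because the stop date cannot be recovered by analysis later.

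**What to change.** 1. Name the ITULAZAX stop date and the reason for stopping as data to be recorded at withdrawal. Where no stop date exists for a patient known to have stopped, use the withdrawal date and disclose this. It can only fall on or after the true stop, so some upward bias would remain.
2. State that intake after a known stop counts as zero and is not missing data, so that the rule in Section 7.4 does not apply to it.
3. Report adherence in the whole Safety Set, with persistence beside it: time to stopping ITULAZAX, with reasons, and with patients lost to follow-up censored. Patients whose follow-up ends while still on treatment should also be censored and not counted as stoppers. Keep intake while on treatment as a supporting figure.
4. Reconcile the adherence window between Section 3.2.2 (4-6 months) and Section 3.4 (4 months). Report persistence at 4 months, and at 6 months only as far as follow-up allows, because Section 3.1 expects 4 months on average and says that "the number of visits and the duration between the visits are only intended as a guide".

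The cost is a few sentences, one field on the withdrawal page if it is not already there, and one extra table. The downside is that reported adherence will be lower.

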3.3 Study milestones

The planned dates for study milestones are summarised in Table 3.

Table 3 Study milestones

Planned first patient first visit:	Mar 2020
Planned last patient last visit:	Jun 2022
Planned final study report	Jun 2023

For PASS incl. below milestones:

Milestone	Planned date
Start of data collection	March 2020
End of data collection	June 2022
Registration in the EU PAS register	September 2019
Final report of study reports	June 2023

3.4 Discussion of design

Aim of the study is to gain information on safety and tolerability and to confirm the known safety profile of ITULAZAX from the clinical development program within a real-life setting.

As this is a non-interventional PASS, potential confounding factors cannot be ruled out. Data collection will reflect routine clinical practice rather than mandatory assessments at pre-specified time points. This may have an impact on the amount of data and the interpretation. Since this is an open-label design, the knowledge of active treatment may affect both investigator-perceived and patient-reported data. The recording of data by physicians in an eCRF allows immediate access to the data and processing of queries.

The strength of the study is that it is able to generate data on safety and tolerability for treatment with ITULAZAX in the real-life setting and in real-life patients with demographics and disease-related characteristics consistent with populations seen in clinical practice.

The sum of pre-specified local adverse drug reactions (including lip swelling/oedema, mouth oedema, palatal oedema, swollen tongue/oedema, oropharyngeal swelling (oedema, pharyngeal oedema/throat tightness, laryngeal oedema) as primary endpoint and number of treatment-related AEs, number of systemic reactions, number of non-local reactions, number of

Template
TPL48761
Signature: OnPaper

serious AEs (SAEs), sum of pre-specified local adverse drug reactions within the first 4 months of treatment in the group of patients with data on Pollen food syndrome (PFS) and adherence to the first 4 months of treatment are suited to address the safety and tolerability in real-life as objective of the study

3.5 Study population

A total of approximately 1000 adult patients are planned to be included in the study. A planned number of 50 investigators in Germany, 80 in the Netherlands, 10-12 in Denmark, 10-12 in Sweden, 10-12 in Norway, 10-12 in Finland are expected to participate.

The decision to initiate treatment with ITULAZAX will be made at the discretion of the investigator before and independently from the decision to include the patient in the study.

The patients will not receive compensation for their participation.

3.5.1 Selection criteria

At the discretion of the investigator, enrolment can be offered to patients:

- Who are prescribed ITULAZAX according to the nationally approved SmPC

In addition, enrolment requires that a written informed consent is obtained before any study-related activities.

3.5.2 Patient discontinuation

The patients will be advised that he/she have the right to discontinue from the study at any time without prejudice.

Furthermore, the patient may also be discontinued from the study at the discretion of the investigator, e.g. in case of AEs or treatment discontinuation.

In case of discontinuation, the investigator should attempt to collect any outstanding data, if possible. The investigator should inquire about the reason for discontinuation (adverse event, non-compliance with protocol or other) and specify this in the case report form (refer to Section 4).

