Time frame	Day 0	1-3 months after V1	1-3 months after V2	1-3 months after V3
Visit window	± 10 days	± 10 days	± 10 days	± 10 days
Informed consent	X			
Demography and body measurements	X			
Patient eligibility	X			
History of allergy (incl. PFS)	X			
Diagnostics, as far as available	X			
Previous (completed) immunotherapy(ies)	X			
Concomitant immunotherapy(ies)	X	X	X	X
Relevant previous and concomitant medication	X	X	X	X
Previous and concomitant illness	X	X	X	X
Allergy symptoms	X	X	X	X
PFS-symptoms	X	X	X	X
Symptomatic medication	X	X	X	X
Antibody Responder Test (ART), if performed		(X)	(X)	(X)
Handout of patient videos about AIT/side effects	(X)	(X)	(X)	(X)
Fractionated exhaled Nitric oxide (FeNO), if	(X)	(X)	(X)	(X)

performed				
First administration of ITULAZAX	X			
Assessment of AEs	X	X	X	X
Global assessment of tolerability at final visit			(X)	X
Study completion/withdrawal	(X)	(X)	(X)	X

1 Introduction

ITULAZAX achieved marketing authorization for sublingual allergy immunotherapy in adult patients with allergic rhinitis due to allergens from the birch homologous group in July 2019 in Denmark, Germany, Norway and Sweden, and in August 2019 in Finland and in the Netherlands after a clinical development program comprising clinical trials in phase 1 to 3. The current non-interventional PASS is conducted to record first data on safety and tolerability of ITULAZAX during routine treatment in real-life.

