In general, treatment was well tolerated. The most frequently reported treatment-related adverse events (TRAEs) were mild-to-moderate local reactions related to sublingual administration of the tablet, the most common events were oral pruritus and throat irritation. Twenty-five (8%) subjects in ITULAZAX group discontinued the trial because of 98 AEs. These were mainly characterised as irritation or swelling in the mouth or throat of mild or moderate intensity.

The safety and tolerability during routine treatment in real life will be investigated in this Non-interventional-PASS.

The safety and tolerability profile and expected frequencies according to the clinical trials with ITULAZAX are described in the Summary of Product Characteristics (SmPC), [5].

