4.2 Collection, recording and reporting of adverse events

All AEs are systematically collected in this study from the patient has signed informed consent and until end of study defined as last visit 4. These events must be recorded and evaluated via the AE form in the eCRF by the investigator. The investigator should record the diagnosis if available and if not available the symptoms should be recorded separately.

Specific additional reporting requirements are applicable for SAEs and pregnancy related events as further described below. The additional information must be provided according to requested timelines by fax/email to the local affiliate of ALK via:

	Germany	Denmark, Norway, Sweden, Finland	Netherlands
E-Mail	[contact]	[contact]	[contact]
[contact]	[name]	[name]
Emergency [contact]	DK: [name] NO: [name] SE: [name] FI: [name]	[name]
Local safety contact persons	[name], Stufenplanbeauftragte [name], [name]. [name] (beide stellv. Stufenplanbeauftragte)	[name], NPPV [name], deputy NPPV	[name], NPPV [name], [name], deputy NPPVs

If requested, please forward supporting documents to ALK via fax or via e-mail to the appropriate local affiliate (contact details see above). Please state the trial ID (NI-TT-01) and the subject and site ID on all documents.

IMPORTANT: Any information that could reveal the identity of the trial subject must be hidden or removed in the source documentation. Also, information that is not relevant for the subject and the subject's condition must be hidden or removed.

ALK informs the competent authorities and independent ethics committees (IECs) about AEs reported in the study in accordance with local requirements in force.

SAEs

- All SAEs must be reported to ALK via the SAE form provided in the eCRF within 24 hours of obtaining knowledge of the event.
- SAEs must be followed until the outcome of the event is "recovered", "recovered with sequelae", "death" and until all queries have been resolved. For cases of chronic conditions and cancer, follow-up until "recovered", "recovered with sequelae" or

Template
TPL48761
Signature: OnPaper

NI Protocol

“death” is not required. After the subject has completed the study, these cases can be closed with “not recovered”.

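### Section 3.5.2 permits study exit because of an AE or a treatment stop, which conflicts with AE collection to visit 4 and does not separate stopping the tablet from leaving the study

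*Protocol*

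**What the plan says.** Section 3.5.2 gives the patient the right to leave at any time. It then adds that "the patient may also be discontinued from the study at the discretion of the investigator, e.g. in case of AEs or treatment discontinuation". On data at exit it says: "In case of discontinuation, the investigator should attempt to collect any outstanding data, if possible". On the reason it says: "The investigator should inquire about the reason for discontinuation (adverse event, non-compliance with protocol or other) and specify this in the case report form". The word discontinuation is used there without saying whether it means the tablet or the study.

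Section 4.2 has all AEs collected systematically from consent "until end of study defined as last visit 4". It requires SAEs to be followed to outcome, apart from chronic conditions and cancer. Section 4.2.1 keeps AEs that the investigator considers related reportable to the sponsor after the end of the study.

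The flow chart (Table 2) has one row for leaving, "Study completion/withdrawal", which can be completed at any visit. It has no row for the end of treatment. It places the global tolerability assessment at V4 and, in brackets, at V3. Sections 3.7.2 to 3.7.4 each ask at V2, V3 and V4 for an "Adherence estimate (average frequency of tablet intake, reasons for not taking the tablet)".

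**The concern.** In a safety study, an AE and the treatment stop that may follow it are the outcomes of interest. Naming them as example grounds for ending participation lets the outcome decide how long the patient is observed. That is outcome-dependent loss of follow-up. Its likely direction is towards a more favourable picture, because those still under observation are more often those who tolerate the tablet. Data not collected for this reason cannot be recovered by any later analysis rule.

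There is also a recording problem. If leaving the study and stopping the tablet share one event and one reason, the report may be unable to say when the tablet was stopped, or to link the stop to a particular AE.

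**Working it through.** The protocol gives no dropout rate, and its sample size of about 1000 is empirical (section 7.1), so there is no planned figure for loss to reproduce. The check has two parts.

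**Part 1: the sections side by side**

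- *Duration of AE collection.* Section 4.2 runs to visit 4, while section 3.5.2 allows exit before it. Neither says whether AEs are still entered for a patient taken out at, say, month 1. Seeking outstanding data at exit looks back and does not provide for continued collection.
- *AE without a treatment stop.* Section 3.5.2 lists AEs and treatment discontinuation as alternatives. A patient who is still taking the tablet can therefore be removed because of an AE. Later local reactions in that patient would not enter the primary endpoint, which is a sum of events (section 3.2.1), although exposure continues.
- *Denominator.* Section 7.2 keeps everyone with one administration in the Safety Set, and section 7.4 does not replace missing data. An early leaver stays in the denominator and adds no later events.
- *Tolerability rating.* Table 2 allows withdrawal at V1 or V2, but schedules the rating only at V3 (bracketed) and V4. Section 3.7.4 lists it at V4 only. Section 3.8.6 names it among items for visits 2-4 without assigning a visit. A patient who leaves at V1 or V2 has no rating scheduled in the flow chart.
- *Adherence.* The estimate is taken at V2-V4, so a patient who leaves before V2 may have none.
- *Non-serious AEs.* Only SAEs must be followed to outcome. Section 1 expects mostly mild-to-moderate local reactions, and their course can be cut off at exit.
- *Recording.* Section 4.1.3 defines severity, causality and outcome for each AE, but not action taken with the product. No item described in the protocol gives the date of stopping the tablet or links the stop to an AE.
- *Consistency.* The discretion lies with 50 + 80 + 4 × (10 to 12) = 170 to 178 planned investigators (section 3.5), so practice may differ between sites.

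**Part 2: size**

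Inputs from section 1.1 are 634 randomised 1:1, so about 634 / 2 = 317 on active treatment, and 25 who discontinued because of AEs. Planned follow-up is 4-6 months (section 3.1).

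1. Rate: 25 / 317 = 7.9%, which agrees with the printed 8%. The exact (Clopper-Pearson) 95% interval is 5.2% to 11.4%.
2. Applied to 1000 patients (assumption): about 79, with a range of 52 to 114.
3. Worst case: all 79 leave the study at month *m* of a planned *F* months. Share of all person-months lost = 7.9% × (*F* − *m*) / *F*.

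| Leaving at month | Lost in these patients, *F* = 4 | Lost overall, *F* = 4 | Lost in these patients, *F* = 6 | Lost overall, *F* = 6 |
|---|---|---|---|---|
| 0.5 | 3.5/4 = 88% | 6.9% | 5.5/6 = 92% | 7.2% |
| 1 | 3/4 = 75% | 5.9% | 5/6 = 83% | 6.6% |
| 2 | 2/4 = 50% | 4.0% | 4/6 = 67% | 5.3% |

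4. At the limits of the interval, the overall loss runs from 5.2% × 50% = 2.6% to 11.4% × 92% = 10.5%.

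These are person-months of observation of any kind. For patients who have stopped the tablet, most of that time is off treatment and adds little at-risk time for reactions to its intake.

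**The case against.** The strongest reply is that the text permits exit and does not require it, and that safeguards exist. Outstanding data are sought, SAEs are followed to outcome, related AEs after the study remain reportable, and nobody leaves the Safety Set. A reaction that leads to exit has already been counted. Section 7.4 summarises AEs during administration, and once the tablet is stopped new local reactions to it are not expected, so the primary endpoint loses little. The study is descriptive, its visit schedule is only a guide (section 3.1), and section 3.4 admits that routine data collection limits interpretation.

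Most of this stands, and it rules out three stronger readings.

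- A reader might infer that stopping because of an AE goes unrecorded. It does not: section 3.5.2 names adverse event as a reason, and V2-V4 ask why tablets were not taken.
- A reader might infer that observation will end earliest in patients who react. The text makes this possible, not certain.
- A reader might infer that no comparison with the pivotal trial is possible. Section 1.1 reports that "Twenty-five (8%) subjects in ITULAZAX group discontinued the trial because of 98 AEs". That is trial discontinuation with an AE reason, and the reason field in section 3.5.2 can supply a broadly similar count.

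The reply does not reach the patient removed for an AE while still on the tablet, the cut-off course of non-serious AEs, the missing tolerability ratings and adherence estimates, or the mismatch with section 4.2.

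**Conclusion.** The point holds as a limited one. Section 3.5.2 conflicts with section 4.2 on how long AEs are collected. It makes the outcome under study a permitted reason to stop observing, and it does not separate stopping the tablet from leaving the study. Where investigators use the permission, the global tolerability rating, the adherence estimate and the course of non-serious AEs lean towards patients who tolerate the tablet. The primary endpoint is affected mainly through patients removed while still exposed, and the documents give no figure for how many there would be.

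The size is about 79 of 1000 patients and 4-7% of planned person-months. It assumes that the pivotal trial's rate carries over to routine care and, as a worst case, that every such patient leaves the study at 0.5-2 months. The overall loss is small but concentrated in patients who reacted. It does not invalidate the study. It is worth correcting because the correction is cheap and the lost data cannot be recovered.

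**What to change.** 1. In section 3.5.2, delete the two examples (AEs and treatment discontinuation) as grounds for ending study participation. Keep the patient's right to withdraw.
2. State that stopping the tablet, whenever that is decided in routine care, does not by itself end data collection.
3. For such patients, enter AE data and the global tolerability rating from the remaining routine contacts, or in one closing eCRF entry.
4. Record date and reason of stopping the tablet separately from date and reason of leaving the study, and link the former to the AE where there is one.
5. Reconcile sections 3.5.2 and 4.2 on when AE collection ends for a patient who does not reach visit 4. Section 3.1 already allows for three visits only.

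The cost is a wording change, one eCRF item, and one closing entry for each patient who stops (about 79 if the pivotal rate applies). Some closing entries will stay missing because patients do not return. No extra visit is imposed, so the study remains non-interventional, and no treatment decision is changed.
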